**Table 3. Treatment-Related Thrombocytopenia and Bleeding**

Event	CTCAE (v4.03) Grade	Management/Action
Thrombocytopenia	2  (Management required only for patients starting with normal platelet counts; patients starting with grade 1 or 2 thrombocytopenia at Baseline do not require dose adjustments)	

Reduce to 50% of the prior dose

	3  (Management required only for patients starting with normal platelet count or grade 1 thrombocytopenia; patients starting with grade 2 or 3 thrombocytopenia at Baseline do not require dose adjustments)	

Hold pacritinib/placebo. If the toxicity resolves to Baseline grade within 7 days, treatment may be resumed at the same level or at 50% of the dose. If the toxicity does not resolve or if it occurs at the lowest dose level, pacritinib/placebo must be discontinued.

If criterion is met on the day of hospital discharge, pacritinib/placebo should not be administered as an outpatient.

	4  (Management required only for patients starting with normal platelet count or grade	

Hold pacritinib/placebo. If the toxicity resolves to Baseline grade within 7 days, treatment may be resumed at the same level or at 50% of the dose. If the toxicity does not resolve

**Table 3. Treatment-Related Thrombocytopenia and Bleeding**

Event	CTCAE (v4.03) Grade	Management/Action
	1 or 2 thrombocytopenia; patients starting with grade 3 or 4 thrombocytopenia at Baseline do not require dose adjustments)	or if it occurs at the lowest dose level, pacritinib/placebo must be discontinued. 

• If criterion is met on the day of hospital discharge, pacritinib/placebo should not be administered as an outpatient.

Bleeding	1	

• No change

	2	

• Hold pacritinib/placebo until bleeding resolves for up to 2 days. Restart pacritinib/placebo at the same dose. If bleeding recurs, hold again for up to 2 days and restart at 50% of the prior dose.

• If bleeding is ongoing after 2 days, discontinue pacritinib/placebo.

• If treatment-related bleeding grade 2 or higher occurred on study, pacritinib/placebo should not be administered as an outpatient.

	3	

• Hold pacritinib/placebo until bleeding resolves for up to 2 days. Restart pacritinib/placebo at 50% of the prior dose. If bleeding recurs, hold again for up to 2 days and restart at 50% of the prior dose.

• If bleeding is ongoing after 2 days, discontinue pacritinib/placebo.

• If treatment-related bleeding grade 2 or higher occurred on study, pacritinib/placebo should not be administered as an outpatient.

	4	

• Discontinue pacritinib/placebo.

Abbreviations: CTCAE = Common Terminology Criteria for Adverse Events.

Dose interruptions and modifications for SOC agents will be based on the prescribing information described in the most current versions of the agents' approved labeling.

#### **6.5.4 Dosage Management Guidelines for QTcF Interval Prolongation**

An ECG will be performed at Screening (Baseline), Days 3, 8, 15 (or End of Treatment [EOT]), 22, 28, and on the day of hospital discharge (for patients who will be continuing pacritinib/placebo as outpatient), and as clinically indicated.

Treatment should be modified as shown in [Table 4](#), as recommended by FDA in case of QTcF interval prolongation. Dose modifications for any instance of QTcF prolongation (irrespective of relationship to study drug) are also described in this section. Dose levels referenced in the

following tables refer to the following available doses: 200 mg BID, 100 mg BID, and 100 mg QD.

**Table 4. QTcF Prolongation**

CTCAE (v4.03) Toxicity Grade	Management/Action
1	

• No change

2	

• No change

3 (including QTcF $\geq$ 501 on any occasion)	

• For QTcF <math>\geq</math> 501 msec on any assessment, hold pacritinib/placebo and assess daily ECGs while inpatient until toxicity resolves to grade <math>\leq</math> 2 (QTc <math>\leq</math> 500 msec). If toxicity resolves to grade <math>\leq</math> 2, treatment may be resumed. If this is the second occurrence, the dose must be reduced by 50%. If already at the 100 mg QD dose, discontinue pacritinib/placebo.

• If the QTcF on the date of discharge is <math>>500</math> msec, pacritinib/placebo cannot be administered in an outpatient setting.

4	

• Discontinue pacritinib/placebo

Abbreviations: CTCAE = Common Terminology Criteria for Adverse Events; ECG = electrocardiogram; QD = once daily; QTcF = QT corrected by the Fridericia method.

Electrolyte repletion should be considered for patients who have electrolyte levels below the lower limit of normal upon entry into the study or while receiving pacritinib/placebo.

#### **6.5.5 Dosage Management Guidelines for Diarrhea**

Treatment with antidiarrheals such as loperamide (Imodium®) is advised for all patients who experience new onset diarrhea (Table 5). Dose levels referenced in the tables refer to the following available doses: 200 mg BID, 100 mg BID, and 100 mg QD.

**Table 5. Dosage Management for Treatment-Related Diarrhea**

CTCAE (v4.03) Toxicity Grade	Management/Action
1 or 2	

• No change

3	

• Hold pacritinib/placebo. If the toxicity resolves to grade <math>\leq 1</math> or to the Baseline grade within 7 days, treatment may be resumed at the same level or at 50% of the dose. Concomitant antidiarrheal treatment is required for patients restarting pacritinib/placebo. If the toxicity does not resolve or if it occurs at the lowest dose level, pacritinib/placebo must be discontinued.

4	

• Hold pacritinib/placebo. If the toxicity resolves to grade <math>\leq 1</math> or to the Baseline grade within 7 days, treatment may be resumed at 50% of the dose. Concomitant antidiarrheal treatment is required for patients restarting pacritinib/placebo. If the toxicity does not resolve or if it occurs at the lowest dose level, pacritinib/placebo must be discontinued.

Abbreviations: CTCAE = Common Terminology Criteria for Adverse Events.

#### **6.5.6 Dosage Management Guidelines for Treatment-Related Toxicities Other than QTcF Prolongation, Diarrhea, Bleeding, or Thrombocytopenia**

Treatment should be modified as shown in [Table 6](#) in the event of related nonhematologic toxicities other than QTcF prolongation or diarrhea. Dose levels referenced in the following tables refer to the following available doses: 200 mg BID, 100 mg BID, and 100 mg QD.

**Table 6. Treatment Toxicity and Dosage Management: Treatment-Related Toxicities Other than QTcF Prolongation, Diarrhea, or Thrombocytopenia**

CTCAE (v4.03) Toxicity Grade	Management/Action
1 or 2	

• No change

3	

• Hold treatment

• If the toxicity resolves to grade <math>\leq 1</math> or to the Baseline grade within 7 days, treatment may be resumed at the same level or at the 50% dose level, at the discretion of the investigator. Otherwise, treatment should be discontinued.

4	

• Hold treatment

• If the toxicity resolves to grade <math>< 1</math> or to the Baseline grade within 7 days, treatment may be resumed, but dosage will be reduced to 50% from the level at which the toxicity was observed. If grade 4 toxicity occurs at the lowest dosage of 100 mg QD or if there is no resolution within 7 days, the patient should be discontinued from pacritinib/placebo.

Abbreviations: CTCAE = Common Terminology Criteria for Adverse Events; QD = once daily; QTcF = QT corrected by the Fridericia method.

## 6.6 Concomitant and Excluded Therapies

Treatment with cytoreductive therapy is not permitted during the assigned treatment period. Pacritinib is metabolized by the P450 system, including cytochrome P450 3A4 (CYP3A4). Use of strong CYP3A4 inhibitors is not permitted as these can lead to significantly increased concentrations of pacritinib. Use of strong cytochrome P450 (CYP450) inducers is not permitted as these can lead to significantly reduced concentrations of pacritinib. Lists of selected strong CYP3A4 inhibitors and P450 inducers are found in [Appendix 1](#) and [Appendix 2](#), respectively.

Concomitant use of investigational agents (those administered as part of a clinical trial) for the treatment of COVID-19 is prohibited with the exception of antiviral agents. The use of IL-1 or IL-6 blocking immunomodulatory agents (such as tocilizumab, canakinumab, sarilumab, anakinra) is allowed if, in the opinion of the investigator, a patient is clinically deteriorating. However, patients who require IL-1 or IL-6 blocking agents must be discontinued from study drug. Hydroxychloroquine, chloroquine, azithromycin, corticosteroids, and antiviral agents are permitted concomitant medications.

Electrolyte repletion should be considered for patients who have electrolyte levels below the lower limit of normal upon entry into the study or while receiving pacritinib/placebo.

Patients who develop worsening gastrointestinal symptoms with the initiation of pacritinib/placebo treatment may be treated with standard antidiarrheal and/or anti-emetic medications (Section [6.6.1](#)).

Treatment-dose anticoagulation and anti-platelet therapy may be administered after randomization, if required; patients do not need to discontinue pacritinib/placebo if one of these medications is initiated. However, patients should not receive such agents concomitant with study drug administration if their platelet counts drop to < 50,000/ $\mu$ L; prophylaxis-dose anticoagulants are permitted for all patients on study. Treatment-dose anticoagulants and anti-platelet agents may be administered at any dose after the study drug treatment period has ended.

Cytotoxic chemotherapy or cancer-directed immunotherapy is prohibited during the pacritinib/placebo treatment period (14 or 21 days). Cancer-directed immunotherapy includes immune checkpoint inhibitors, antibody-based cancer therapy, and cell-based cancer therapy.

### **6.6.1     *Management of Gastrointestinal Toxicity***

The need for managing gastrointestinal effects of pacritinib, particularly diarrhea, should be anticipated. A careful Baseline evaluation of bowel habits (frequency and consistency of bowel movements) should be obtained prior to the first dose.

Loperamide (Imodium®) or a similarly effective antidiarrheal drug may be administered at the Investigator's discretion if changes in frequency or consistency of bowel movements occur after starting pacritinib/placebo.

Early intervention for diarrhea should be initiated for patients with increases of one grade or more in diarrhea ([Appendix 3](#)). Standard supportive care measures to control symptoms of gastrointestinal toxicity such as diarrhea, constipation, and nausea should be provided.

## **7 STUDY ASSESSMENTS**

### **7.1 Criteria for Evaluation**

#### **7.1.1     *Efficacy***

##### **7.1.1.1     *7-Point Ordinal Scale of Clinical Status***

The following 7-point ordinal scale of clinical status ([Cao et al 2020](#)) will be used to assess the ordinal scale secondary endpoints. The ordinal scale score is to be documented daily on study through Day 28 for all patients, including those who have been discharged from the hospital.

1. Not hospitalized with resumption of normal activities
2. Not hospitalized but unable to resume normal activities
3. Hospitalization, not requiring supplemental oxygen
4. Hospitalization, requiring supplemental oxygen not meeting criteria for categories 5 or 6
5. Hospitalization, on non-invasive positive pressure ventilation or high-flow nasal cannula

6. Hospitalization, requiring IMV and/or ECMO
7. Death

#### **7.1.1.2 *Immunomodulatory Agents***

The use of other immunomodulatory agents as treatment for COVID-19, such as corticosteroids, tocilizumab, anakinra, or eculizumab, will be assessed as a secondary endpoint.

#### **7.1.1.3 *Lung Function Assessments***

Lung function will be assessed by SpO2 in ambient air (if possible), SpO2 with oxygen supplementation (if applicable), documentation of oxygen delivery method, highest oxygen delivery flow rate (if receiving non-invasive oxygen), highest fraction of inspired oxygen (%FiO2) (if on continuous positive airway pressure [CPAP], bilevel positive air pressure [BiPAP], or invasive mechanical ventilation [IMV]), highest positive end-expiratory pressure (PEEP; if on positive pressure ventilation), and lowest PaO2:FiO2 ratio (if arterial blood gas [ABG] is obtained and the patient is on positive pressure ventilation).

### **7.1.2 *Safety***

#### **7.1.2.1 *Adverse Events***

AEs will be collected during the clinical study from the time the patient is randomized through 30 days following the last dose of pacritinib/placebo. AEs will be identified and reported to the Sponsor, in addition to any clinically indicated diagnostic, monitoring, treatment, and follow-up measures used to manage the reported AE. Pregnancy alone will not be considered as an AE. Pregnancy will be reported on a Pregnancy Reporting Form (Section 8.1.4.4). Abnormal pregnancy outcomes and/or any AE for the child or fetus (including miscarriage) will be reported as SAEs. Occurrences of overdose will be reported as SAEs.

#### **7.1.2.2 *Hematology***

Hematology parameters, (CBC, WBC, hemoglobin, hematocrit, and platelet count), will be evaluated at Screening (may be performed within 24 hours prior to the start of Screening) and daily from Days 2 through 28 or EOT, and on the day of hospital discharge. WBC differential will be evaluated at Screening (may be performed within 24 hours prior to the start of Screening), Day 8, Day 15 or EOT, Day 22, Day 28, and on the day of hospital discharge. Hematology tests are not required after hospital discharge. Analysis of CBC results will be performed at local laboratories. Results from unscheduled hematology tests should be entered into the electronic database using an Unscheduled Hematology case report form (CRF). Pacritinib/placebo dosage modifications will be implemented for clinically significant AEs identified with this testing per the guidelines for “Treatment-Related Thrombocytopenia and Bleeding” (Section 6.5.3).

### **7.1.2.3      *Coagulation Testing***

Coagulation testing will include international normalized ratio (INR), partial thromboplastin time (PTT), and fibrinogen at Screening (may be performed within 24 hours prior to the start of Screening), Day 8, Day 15 or EOT, Day 22, Day 28, and on the day of hospital discharge. Coagulation tests are not required after hospital discharge. Results from unscheduled coagulation tests should be entered into the electronic database using an Unscheduled Coagulation CRF. Analysis of coagulation results will be performed at local laboratories.

### **7.1.2.4      *Serum Chemistry***

Serum chemistry parameters (sodium, potassium, chloride, bicarbonate, blood urea nitrogen, creatinine, glucose, calcium, and magnesium) will be evaluated at Screening (may be performed within 24 hours prior to the start of Screening) and Day 2 through Day 28 or EOT, and on the day of hospital discharge. Serum chemistry tests are not required after hospital discharge. Results from unscheduled serum chemistry tests should be entered into the electronic database using an Unscheduled Serum Chemistry CRF. Analysis of serum chemistry results will be performed at local laboratories. Pacritinib/placebo dosage modifications will be implemented for clinically significant AEs identified with serum chemistry testing per the guidelines for “Treatment-Related Toxicities Other than QTcF Prolongation, Diarrhea, Bleeding, or Thrombocytopenia” (Section [6.5.6](#)).

### **7.1.2.5      *Liver Function Panel***

Liver function parameters (aspartate aminotransferase [AST], alanine aminotransferase (ALT), alkaline phosphatase, total bilirubin, and albumin) will be evaluated at Screening (may be performed within 24 hours prior to the start of Screening), Day 8, Day 15 or EOT, Day 22, Day 28, and on the day of hospital discharge. Liver function panel tests are not required after hospital discharge. Results from unscheduled liver function panel tests should be entered into the electronic database using an Unscheduled Liver Function Panel CRF. Analysis of serum chemistry results will be performed at local laboratories. Pacritinib/placebo dosage modifications will be implemented for clinically significant AEs identified with serum chemistry testing per the guidelines for “Treatment-Related Toxicities Other than QTcF Prolongation, Diarrhea, Bleeding, or Thrombocytopenia” (Section [6.5.6](#)).

### **7.1.2.6      *ECG Assessment***

An ECG will be performed at Screening (may be performed within 48 hours prior to the start of Screening), Day 3, Day 8, Day 15 or EOT, Day 22, Day 28, and on the day of hospital discharge if before EOT. Eligibility is to be based on QTcF of  $\leq 480$  msec. An ECG will also be performed on the day of hospital discharge if the patient will be continuing pacritinib/placebo as an outpatient; however, ECGs are not required after hospital discharge. Results from unscheduled ECG assessments should be entered into the electronic database using an Unscheduled ECG CRF. ECGs should be assessed using at least 3 leads; rhythm strips from telemetry monitoring are acceptable. Pacritinib/placebo modifications and follow-up monitoring for clinically significant ECG changes will be implemented as per the guidelines for “Dosage

Management Guidelines for QTcF Interval Prolongation” (Section 6.5.4). Additional ECG testing shall be done as clinically indicated.

#### **7.1.2.7 *Markers of Disease Severity***

Blood samples for analysis of markers of disease severity (CRP, ferritin, D-dimer, IL-6, troponin-I, LDH, BNP, procalcitonin, , triglycerides, and CK) will be collected from all patients at Screening (may be performed within 24 hours prior to the start of Screening), before the morning dose on Day 3, Day 8, Day 15 or EOT, Day 22, Day 28, and on the day of hospital discharge. These markers do not need to be assessed after hospital discharge. The assessments for markers of disease severity are required if they can be performed at a local laboratory or if the study center has access to an external laboratory where the samples can be sent for analysis. If a study center does not have access to a local or external laboratory that can perform these assessments, the Investigator must provide written confirmation of the inability to perform the assessment(s), and approval from the CTI Medical Monitor is required to omit the assessment(s). Results from unscheduled tests for markers of disease severity should be entered into the electronic database using an Unscheduled Markers of Disease Severity CRF.

#### **7.1.3 *Informed Consent, Screening, and Washout of Prohibited Concomitant Medications Before Beginning Pacritinib/placebo***

Informed consent must be obtained before any study procedures and Screening evaluations are performed, unless those evaluations are performed as part of SOC. Patients must provide informed consent within 96 hours after hospital admission. Patients who do not meet eligibility criteria at Screening may be rescreened at a later date.

The informed consent process should be documented in the patient’s medical chart.

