## **2.1 Justification of Included Patient Population**

The study population will consist of hospitalized adult patients with severe COVID-19 with or without cancer. Severe COVID-19 is defined as confirmed disease in patients who are hospitalized with hypoxia [ $\text{SpO}_2 \leq 93\%$  on room air], respiratory rate  $>30$ ,  $\text{PaO}_2/\text{FiO}_2 <300$ , but do not require IMV ([NIH COVID-19 Treatment Guidelines 2020](#)). Patients with moderate COVID-19 are not eligible for the study because it is likely that they will not be receiving supplemental oxygen and will not be hospitalized. Patients with critical COVID-19 are not included because the goal of pacritinib therapy is to prevent patients from progressing to the acute respiratory distress syndrome associated with COVID-19.

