## 4 PATIENT SELECTION AND WITHDRAWAL

### 4.1 Target Population

#### 4.1.1 *Inclusion Criteria*

1. Hospitalized or will be hospitalized prior to randomization for the treatment of severe COVID-19 with SARS-CoV-2 infection confirmed by either a) a positive reverse transcriptase polymerase chain reaction (RT-PCR) or b) an antigen-based test from any respiratory, nasopharyngeal, saliva, blood, or stool specimen at Screening or documented within 1 week prior to the start of Screening (Severe COVID-19 is defined as confirmed disease in patients who are hospitalized with hypoxia [ $\text{SpO}_2 \leq 93\%$  on room air], respiratory rate  $>30$ ,  $\text{PaO}_2/\text{FiO}_2 <300$ , but do not require IMV).
2. Age  $\geq 18$  years
3. Platelet count  $\geq 50,000/\mu\text{L}$
4. If fertile, willing to use effective birth control methods during the study
5. Provision of informed consent within 96 hours after hospitalization

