#### **4.1.2     *Exclusion Criteria***

1. In the opinion of the investigator, progression to death is imminent and inevitable within the next 24 hours, irrespective of the provision of treatments
2. Currently intubated or intubated between screening and randomization
3. Suspected active uncontrolled bacterial, fungal, viral, or other infection (besides COVID-19)
4. Prior allogenic hematopoietic stem cell transplantation
5. Active lung cancer or history of lung cancer within the past 12 months
6. Any active grade 2 or higher hemorrhage
7. Any active gastrointestinal or metabolic condition that could interfere with absorption of oral medication
8. Uncontrolled intercurrent illness that, in the judgment of the treating physician, would limit compliance with study requirements
9. Known seropositivity for human immunodeficiency virus with CD4 count < 200/mm^3 within 3 months prior to randomization
10. Pregnant or breastfeeding, or positive pregnancy test in a pre-dose examination
11. Concurrent enrollment in another interventional trial (investigational COVID-19 antiviral studies are permitted)
12. Serum creatinine > 2.5 mg/dL
13. Total bilirubin > 4× the upper limit of normal
14. QT corrected by the Fridericia method (QTcF) prolongation > 480 msec
15. Known history of New York Heart Association Class II, III, or IV congestive heart failure prior to hospital admission
16. Known allergic reaction to any JAK2 inhibitor
17. Exposure to any JAK2 inhibitor within 28 days
18. Currently receiving a strong CYP3A4 inhibitor or strong P450 inducer ([Appendix 1](#) and [Appendix 2](#), respectively) and unable to stop the medication prior to the first dose of study drug and throughout the duration of study drug administration
19. Treatment with cytoreductive chemotherapy administered within 14 days prior to randomization

20. Administration of an IL-1 or IL-6 blocking immunomodulatory agent (such as tocilizumab, canakinumab, sarilumab, anakinra) within 48 hours prior to randomization
21. Currently receiving therapeutic anticoagulation or anti-platelet medication and unable to stop the medication prior to randomization. Prophylactic anticoagulation therapy or aspirin ( $\leq 100$ mg) are permitted.
22. Unable to ingest capsules or tablets at randomization

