#### **7.1.4 *Summary of Study Assessments and Events by Day***

##### **7.1.4.1 *Screening (Study Day -1 or 1)***

The Screening evaluations listed below are to be carried out between Day -1 and Day 1 (prior to the start of treatment). Screening and randomization may occur on either Day -1 or Day 1. Patients may be screened, randomized, and started treatment on the same day (Day 1).

- Signing of ICF within 96 hours after hospital admission
- Demographics (age, sex, race, and ethnicity)
- Medical history
- Vital signs (blood pressure, pulse, respiratory rate, temperature, SpO2, and body weight)
- 7-point ordinal scale of clinical status
- SpO2 in ambient air (if possible)

- SpO2 with oxygen supplementation (if applicable)
- Highest %FiO2 (if on CPAP, BiPAP, or IMV)
- Highest PEEP)( if on positive pressure ventilation)
- ECG (at least 3 leads; may be performed within 48 hours prior to the start of Screening)
- Serum chemistry, including sodium, potassium, chloride, bicarbonate, blood urea nitrogen, creatinine, glucose, calcium, and magnesium (The results of laboratory assessments performed in the emergency room [ER] or upon hospital admission that are relevant for the determination of eligibility may be used to confirm eligibility provided that they have been performed within 24 hours prior to the start of Screening.)
- Liver function panel, including aspartate aminotransferase (AST), alanine aminotransferase (ALT), alkaline phosphatase (ALP), total bilirubin, and albumin (The results of laboratory assessments performed in the ER or upon hospital admission that are relevant for the determination of eligibility may be used to confirm eligibility provided that they have been performed within 24 hours prior to the start of Screening.)
- CBC, including WBC count, hemoglobin, hematocrit, and platelet count (The results of laboratory assessments performed in the ER or upon hospital admission that are relevant for the determination of eligibility may be used to confirm eligibility provided that they have been performed within 24 hours prior to the start of Screening.)
- WBC differential (The results of laboratory assessments performed in the ER or upon hospital admission that are relevant for the determination of eligibility may be used to confirm eligibility provided that they have been performed within 24 hours prior to the start of Screening.)

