- SARS-CoV-2 RT-PCR test or an antigen-based test from any respiratory, nasopharyngeal, saliva, blood, or stool specimen at Screening or documented within 1 week prior to the start of Screening
- Coagulation tests, including INR, PTT, and fibrinogen
- CRP
- Ferritin
- D-dimer
- IL-6
- Troponin-I
- LDH

- BNP
- Procalcitonin
- Triglycerides
- CK
- Serum pregnancy test for women of childbearing potential prior to randomization, which may be performed at any time after arrival to the emergency room or hospital admission
- Chest imaging assessments performed in the ER or upon hospital admission may be used for screening documentation.
- Documentation of oxygen delivery method, which may include nasal cannula, non-rebreather, non-invasive positive pressure ventilation (eg, CPAP or BiPAP), or IMV
- Concomitant medications

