### **6.1 Primary Efficacy Endpoint**

The primary endpoint is the proportion of patients with progression to IMV and/or ECMO or death by Day 28 (+/- 2 days) for the Intent-to-Treat (ITT) Population. Patients will be considered to have progression to IMV and/or ECMO or death based on the [Cao et al. \(Table 3\)](#) clinical status assessment of 6 or 7. Specifically, the proportion of patients with progression to IMV and/or ECMO or death by Day 28 (+/- 2 days) will be calculated in each treatment arm as:

- (Number of patients with clinical status of 6 or 7 at any time on or before Day 28 (+/- 2 days)) / (Number of patients in the ITT population)

Patients who discontinued early and did not progress to IMV and/or ECMO or death (a clinical status of 6 or 7) will be considered as having progression unless they were discharged from the clinical facility (discharge date is not missing), in which case they will be considered non-progression.

Patients will be summarized based on the randomized (planned) treatment arm. Patients can meet this endpoint in two ways by progressing to IMV and/or ECMO or dying.

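### Exclusion 2 looks back only to screening, so a patient ventilated and extubated earlier in the same COVID-19 illness can enter a trial of preventing ventilation

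*Protocol*

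**What the plan says.** **Eligibility.** Exclusion 2 (protocol 4.1.2, worded the same in the synopsis) reads "Currently intubated or intubated between screening and randomization". Section 7.1.4.1 places screening on Day -1 or Day 1. The only time limit on entry is inclusion 5: "Provision of informed consent within 96 hours after hospitalization".

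**Intent.** Section 2.1 explains the target population: "Patients with critical COVID-19 are not included because the goal of pacritinib therapy is to prevent patients from progressing" to COVID-19-related acute respiratory distress syndrome.

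**Rescreening.** Section 7.1.3: "Patients who do not meet eligibility criteria at Screening may be rescreened at a later date". It limits neither the number of rescreens, nor the interval, nor the time since admission. Section 7.1.4.1 lists "Signing of ICF within 96 hours after hospital admission" among the screening items but does not say whether a rescreen repeats that step.

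**Endpoint.** Protocol 11.1.1 counts IMV, ECMO or death in the 28 days after randomization. The numerator in SAP 6.1 is the number of patients with "clinical status of 6 or 7 at any time on or before Day 28" (with a 2-day window), and it names no starting point.

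**The concern.** The primary endpoint is progression to IMV, ECMO or death. A patient who has already been on a ventilator in this illness has had one of those events before entry. The eligibility text sets out to keep the population upstream of that event, but checks only the present and roughly the preceding day.

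Two things follow if such patients are enrolled:

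- The population is no longer the one section 2.1 describes. For some patients the outcome becomes re-intubation or death, and the effect of the drug on that may differ from its effect on a first intubation. If it is smaller, the contrast between arms is diluted.
- With no lower bound on the SAP's event count, a status of 6 recorded at an earlier failed screening is not explicitly kept out of the numerator.

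**Working it through.** **1. Does any criterion catch earlier ventilation?**

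- *Exclusion 2* covers current intubation and the interval from screening to randomization. It does not reach back before screening, and it does not name ECMO.
- *Inclusion 1* defines severe disease as not requiring IMV. This describes present status.
- *Baseline score of 3 to 5* (protocol 11.1.1). Also present status.
- *Exclusion 22* tests the ability to ingest capsules or tablets at randomization. An extubated patient may pass.
- *Exclusion 3* (other uncontrolled infection) and the requirement for a positive test at Screening or in the week before it remove some such patients, but not all.
- *Inclusion 5* limits the time of consent. A patient can be intubated, extubated and first screened within 96 hours of admission.

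None of the 22 exclusions addresses IMV that began and ended before screening. The gap therefore exists without any rescreening.

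**2. What does rescreening add?** Two readings are open.

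- If a rescreen needs fresh consent, the 96-hour rule confines it to about the first four days. If the first consent stands, no limit is stated.
- If exclusion 2 means the first screening, a patient intubated after it stays excluded. If it means the latest one, the look-back restarts.

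Only the looser reading of both lets someone who failed screening because of intubation come back much later, after extubation. Screening such a patient is conceivable: the screening list provides for "Documentation of oxygen delivery method, which may include nasal cannula, non-rebreather, non-invasive positive pressure ventilation (eg, CPAP or BiPAP), or IMV", and 13.2 allows a legally authorized representative to sign.

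**3. SAP event count.** SAP 7.4.1 takes time to event as the earliest date of status 6 or 7, minus the randomization date, plus 1. A status 6 recorded three days before randomization would give -3 + 1 = -2 days. By contrast, ventilator-free days (SAP 6.2.1) are bounded from Day 1 to Day 28.

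**4. The plan's sample size.** Inputs (protocol 11.6, SAP 3.4): 26.5% versus 13.5%, one-sided 0.10, 80% power, 1:1.

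- Uncorrected: n = [1.2816·√(2·0.20·0.80) + 0.8416·√(0.265·0.735 + 0.135·0.865)]² / 0.13² = 84.5, so 85 per arm (170 in total).
- Continuity-corrected: (84.5/4)·[1 + √(1 + 4/(84.5·0.13))]² = 99.2, so 100 per arm (200 in total).

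The stated 200 reproduces with the correction.

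**5. Dilution, as an illustration.** The documents give neither the share k of previously ventilated patients nor their event rate r. Assume no treatment effect in them and r = 40% in both arms. The arm rates become (1-k)·0.265 + k·0.40 and (1-k)·0.135 + k·0.40. With n = 100 per arm,

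power = Φ{(difference - c - 1.2816·s0)/s1},

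where s0 = √(2·p̄(1-p̄)/n), p̄ is the mean of the two rates, s1 = √([p1(1-p1) + p2(1-p2)]/n), and c = 1/n with the correction or 0 without.

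| Share k | Patients of 200 | Rates | Difference | Power, corrected | Power, uncorrected |
|---|---|---|---|---|---|
| 0 | 0 | 26.5% v 13.5% | 13.0 points | 80.3% | 84.9% |
| 2% | 4 | 26.8% v 14.0% | 12.7 points | 78.5% | 83.3% |
| 5% | 10 | 27.2% v 14.8% | 12.35 points | 75.7% | 80.9% |
| 10% | 20 | 27.9% v 16.2% | 11.7 points | 70.9% | 76.5% |

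If r runs from 50% down to 26.5%, corrected power is 78.3% to 78.8% at a 2% share, 75.2% to 76.5% at 5%, and 69.9% to 72.4% at 10%.

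**The case against.** **Few such patients would get in.** A recently extubated patient must still meet the severe-disease definition, swallow capsules, have no other uncontrolled infection and have a recent positive test. This stands, and it is why the effect is probably small. It does not close the gap.

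**The 96-hour rule caps rescreening.** A reader might infer that rescreening is open-ended and lets ventilated patients return at any point in their stay. The documents do not establish that. Consent is listed as a screening step, the 96-hour sentence directly precedes the rescreening sentence, and exclusion 2 does not say which screening it means. The text is silent on these points, which calls for clarification but does not prove an unlimited route.

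**Admitting extubated patients is a legitimate choice.** They are no longer on a ventilator, and they can be re-intubated or die, so it would be too strong to say that they cannot contribute to the primary question. That is fair. But the protocol does not make this choice openly, and its rationale points the other way.

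**The SAP's meaning is clear.** It speaks of progression, measures time to event from randomization, mentions post-baseline assessments in Table 6 and plans no change from the protocol (SAP 9). A reader might infer that earlier ventilation will be scored as an outcome. Read as a whole, the documents do not intend that. What stands is that the numerator formula and the earliest-date rule state no lower bound.

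**The power loss depends on the correction.** The primary test is Cochran-Mantel-Haenszel with no correction stated. Without one, power is still 80.9% at a 5% share. This stands.

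**Conclusion.** The concern holds in a limited form. On its wording, exclusion 2 admits a patient who was ventilated and extubated earlier in the same illness, and this does not match the reason section 2.1 gives for the population. Undated rescreening may enlarge the group but does not create it, so a rescreening deadline alone would not cure it.

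The size cannot be derived from the documents. On the stated assumptions, a 2% to 5% share costs about 2 to 5 points of corrected power (80.3% to 78.5% or 75.7%), and slightly less uncorrected (84.9% to 83.3% or 80.9%). The shares, the 40% event rate and the absence of effect are assumptions. The sample size calculation itself is sound on its stated inputs.

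A reader might also infer bias between arms. That is not supported: randomization balances these patients in expectation. The cost is a blurred target population and some dilution. The missing lower bound in the SAP is a real but secondary mismatch with protocol 11.1.1.

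**What to change.** 1. **Exclusion 2 (4.1.2 and synopsis).** Reword to exclude patients who received IMV or ECMO at any time during the current COVID-19 illness before randomization.
2. **Section 7.1.3.** State which screening the eligibility checks refer to for a rescreened patient, and whether the 96-hour consent clock applies afresh or the first consent stands. A hard rescreening deadline is not needed. It would also shut out patients who failed for a passing reason, such as the 48-hour washout in exclusion 20.
3. **SAP 6.1 and 7.4.1.** Count only a status of 6 or 7 recorded after randomization and by Day 28, to match protocol 11.1.1. Anchor the bound to randomization rather than Day 1, because SAP 7.1.1 sets Day 1 at first dose and notes that randomization may come earlier.

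The cost is about a sentence in each place and the loss of a few extubated patients. If enrollment has closed, item 3 can still be made before the primary analysis.
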